3.0 PATIENT SELECTION

Inclusion criteria

1. Signed informed consent indicating that patients are aware of the investigational nature of this study, in keeping with the policies of MDACC, must be obtained prior to any study specific procedures.
2. Patients with a histologically confirmed diagnosis of MDS by World Health Organization (WHO) classification and lower-risk MDS as defined by the IPSS classification² (Low or Int-1 disease) or R-IPSS classification¹² (Very Low or Low) are eligible. Patients with MDS/MPD overlap syndromes including CMML are also eligible if they have Low or Int-1 disease per IPSS. Patients may have received MDS-directed therapy (i.e. lenalidomide), although patients with prior exposure to hypomethylating agents (e.g. 5-azacitidine or decitabine) are not eligible.
3. The interval from prior treatment to time of study drug administration is at least 1 week (except for hydroxyurea or steroid therapy) with recovery from all prior therapy-related toxicities
4. Age ≥ 18 years old.
5. Eastern Cooperative Oncology Group (ECOG) performance status of 0 to 2.
6. Adequate liver function, as evidence by serum bilirubin $\leq 2x$ the laboratory normal range (except for patients with Gilbert's Disease), or an aspartate aminotransferase (AST) or alanine aminotransferase (ALT) of $\leq 2.5x$ the upper limit of normal (ULN) or $\leq 5x$ ULN if hepatic disease involvement is present as determined by the investigator.
7. Serum creatinine (Cr) $\leq 2x$ ULN or 24-hour creatinine clearance ≥ 50 ml/min
8. Subjects of reproductive potential must agree to the use of acceptable contraceptive methods for the duration of the time on study and a further 6 months after completion of treatment. Women of childbearing potential must have a negative blood or urine pregnancy test within 72 hours of start of treatment.

Exclusion criteria

1. Subjects with any prior exposure to the hypomethylating agents (5-azacitidine or decitabine) are excluded.
2. Subjects with any prior exposure to JAK2 inhibitor therapy (i.e. ruxolitinib or prior pacritinib therapy) are excluded.

3. Any prior or coexisting medical condition that in the investigator's judgment will substantially increase the risk associated with the subject's participation in the study.
4. Psychiatric disorders or altered mental status precluding understanding of the informed consent process and/or completion of the necessary study procedures.
5. Active uncontrolled serious infection or sepsis at study enrollment. Patients receiving antibiotics for infections that are under control may be included in the study.
6. Gastrointestinal disorders that may significantly interfere with absorption of study drug.
7. Subjects have received potent CYP3A inhibitors within 7 days prior to the initiation of study treatment.
8. History of myocardial infarction, severe/unstable angina, or symptomatic congestive heart failure (New York Heart Failure (NYHA) Class III or IV congestive heart failure) within 6 months prior to study enrollment or LVEF <50%
9. Impaired cardiac function including ongoing cardiac dysrhythmias of Grade ≥ 2 , ejection fraction < 50%, atrial fibrillation of any grade, or QTc prolongation > 450 ms, or other factors that increase the risk of QT prolongation (i.e. family history of long QT interval syndrome, hypokalemia defined as serum potassium < 3.0 mEq/L)
10. Diagnosis of other malignancies within the last 3 years other than curatively treated non-melanoma skin cancer, carcinoma in situ of the cervix, organ-confined or treated non-metastatic prostate cancer, in situ breast carcinoma after complete surgical resection, or superficial transitional cell bladder carcinoma.
11. Known active Hepatitis A, B or C.
12. Known HIV seropositivity.
13. Women who are pregnant or lactating.

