- **Cardiac:** QTc prolongation has been reported in association with pacritinib therapy. A post-hoc review of the patients in the phase 1-2 Studies SB1518-2007-001 and SB1518-2008-003 identified 9 patients with at least one reported QTc exceeding 500 ms; all but one were treated at a pacritinib dose of ≥ 400 mg QD. Therapy was continued in most of these patients for extended periods of time after the observations of QTc prolongation. In addition, pre-study cardiac history was noted in 7 patients, and 8 patients were taking concomitant medications associated with QTc prolongation. Other cardiac TEAEs and ADRs were rare in all pacritinib-treated populations. Based on these observations, investigators are advised to exclude any patient with a baseline QTc > 450 ms and to perform routine ECG monitoring during treatment. For patients with identified changes in treatment-emergent ECG abnormalities or other cardiac events, study drug may be interrupted or the dose may be reduced per protocol.
- **Hepatic:** Animal studies suggest that pacritinib treatment may cause dose-related hepatotoxicity. There has been little evidence of hepatotoxicity in clinical trials to date. Significant increases in aminotransferases have been observed infrequently and have not been accompanied by concomitant increases in bilirubin. Most reported hepatic toxicities were seen in the myeloid population. No instances of hepatic dysfunction meeting Hy's Law criteria have been observed. Hepatic function (AST/SGPT, ALT/SGOT, alkaline phosphatase, and total bilirubin) will continue to be assessed at frequent intervals during treatment with pacritinib.
- **Renal:** Animal studies suggest that treatment may cause dose-related renal toxicity. To date, little impact on renal function has been observed in human clinical trials. Assessment of renal function (creatinine, BUN, sodium, potassium) will be undertaken frequently in patients participating in clinical trials of pacritinib.

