8.0 PATIENT EVALUATION

Pre-treatment

Results from tests performed as standard of care up to 28 days prior to study entry can be used for determining eligibility and establishing baseline measurements. Any clinically significant abnormal results (except for bone marrow aspiration) should be repeated within 48 hours of beginning therapy to establish a baseline.

- A complete history and physical exam including height, weight, and vital signs (blood pressure, heart rate, breathing rate, and temperature), disease documentation, and performance status (PS) should be performed 72 hours before initiation of study, and subsequently as indicated.
- Document significant baseline abnormalities and concomitant medications within 28 days of initiation of study.
- CBC, platelet count, creatinine, total bilirubin, AST and/or ALT, potassium and blood or urine pregnancy test (when indicated) should be performed 72 hours before initiation of study. Pregnancy testing will be conducted for any female that is of childbearing age that has not been surgically sterilized or without a menses for 12 consecutive months.
- Bone marrow aspirate and/or biopsy during the last 28 days preceding study initiation
- FLT3 and JAK2 mutational status (including FLT3 allelic ratio if mutation present). This can be performed on the pre-study bone marrow aspirate or from peripheral blood
- Cytogenetics will be obtained within 28 days prior to therapy, and should be repeated with all bone marrow assessments performed on study.
- EKG with documentation of QTc interval
- Echocardiogram or MUGA for evaluation of left ventricular ejection fraction
- Pretreatment correlative studies if patient signed for them during consent process.

During Treatment

- CBC, platelet count, creatinine, AST and/or ALT and total bilirubin weekly during first course of therapy, and prior to each course of therapy.
- Document adverse event assessment and concomitant medications at each clinic visit.
- EKG will be performed 4 hours post dosing on cycle 1 day 1 (+/- 1 hour) , on cycle 1 day 28 (+/- 5 days), cycle 4 day 28 (+/- 5 days), and as clinically indicated.
- Bone marrow aspiration on day 28 (+/- 5 days) of Cycle 1 and Cycle 4 of Part 1, and after

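### Inclusion criterion 6 joins the bilirubin and transaminase limits with 'or', so a patient who exceeds one limit but meets the other still satisfies it

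*Combined protocol and SAP*

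**What the plan says.** Section 3.0, inclusion criterion 6, begins "Adequate liver function, as evidence by serum bilirubin" and sets a ceiling of twice the laboratory normal range. The words "except for patients with Gilbert" open an exemption from that ceiling for Gilbert's Disease. The sentence then runs on: "or an aspartate aminotransferase (AST) or alanine aminotransferase (ALT"), with a ceiling of 2.5 times the upper limit of normal (ULN), or 5 times "ULN if hepatic disease involvement is present as determined by the investigator". The word 'and' does not occur in the criterion.

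Three other places bear on it:

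- **Section 3.0, exclusion criteria.** Exclusion 3 bars any condition that, in the investigator's judgment, "will substantially increase the risk associated with the subject"'s taking part. Exclusion 11 reads "Known active Hepatitis A, B or C". Neither contains a bilirubin, AST or ALT value.
- **Section 8.0, Pre-treatment.** The tests due 72 hours before the start include "creatinine, total bilirubin, AST and/or ALT, potassium and blood or urine pregnancy test". This schedules the measurements and sets no limits. Table 8 in Section 9.0 likewise only schedules chemistries.
- **Section 6.0, Observed Risks, Hepatic.** "Animal studies suggest that pacritinib treatment may cause dose-related hepatotoxicity". The same paragraph goes on to report little sign of liver toxicity in clinical trials so far, infrequent aminotransferase rises without accompanying bilirubin rises, and no case meeting Hy's Law.

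**The concern.** The opening words of criterion 6 state its purpose, and bilirubin and transaminases are offered as the evidence. They are not interchangeable measures of one quantity, so normal transaminases do not show that bilirubin is acceptable, or the reverse. Joined by 'or', either result alone satisfies the criterion whatever the other shows.

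What is at stake is consistent, safe entry to the trial. Two investigators could decide differently on the same patient with discordant liver results, and the text would not settle which of them had followed the protocol. The protocol treats liver function as something to watch on this drug, so the entry rule should be unambiguous.

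**Working it through.** No arithmetic from the design applies. The check is a truth table, followed by a search for any text that restates or overrides the criterion.

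**Step 1: the rule as written.** Let B mean that the bilirubin limit is met, G that the patient has Gilbert's Disease, and T that the transaminase limit is met (AST or ALT within the applicable ceiling).

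- As written: (B or G) or T.
- If both limits are required: (B or G) and T.

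**Step 2: a patient without Gilbert's Disease.**

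| Bilirubin limit | Transaminase limit | Criterion 6 as written | If both are required |
|---|---|---|---|
| met | met | satisfied | satisfied |
| met | exceeded | satisfied | not satisfied |
| exceeded | met | satisfied | not satisfied |
| exceeded | exceeded | not satisfied | not satisfied |

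The two readings differ in the two discordant rows. As written, one of the four combinations is rejected. If both limits are required, three are.

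**Step 3: the Gilbert exemption.** If bilirubin must be met, the exemption has a clear job: it keeps a Gilbert patient with acceptable transaminases from being rejected on bilirubin. Under 'or', that patient already qualifies through T, so the exemption is not needed. If it is taken to count the bilirubin branch as met, its only effect under 'or' is to pass a Gilbert patient whose transaminases exceed their limit. The exemption therefore makes sense mainly if the bilirubin limit was meant to bind.

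**Step 4: the raised transaminase ceiling.** Under 'or', the allowance of 5 times ULN for hepatic involvement changes nothing for a patient whose bilirubin is within its limit. It matters only when bilirubin is too high. That is a weaker cue than Step 3, but it points the same way.

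**Step 5: does other text repair it?** Section 8.0 and Table 8 schedule the tests without limits. No exclusion criterion gives a liver value. Exclusion 3 leaves the matter to judgment, and exclusion 11 concerns viral hepatitis only. No section restates criterion 6 in a form that requires both limits.

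**Step 6: the statistical design.** The response and toxicity boundaries, priors and operating characteristics in Section 12.0 do not take criterion 6 as an input. None of them changes.

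**The case against.** The best defence is that the criterion carries its own cue to the intended meaning. The governing requirement is adequate liver function, and the Gilbert exemption presupposes a binding bilirubin limit, so an experienced investigator would probably apply both limits. That is fair, and it is why this is a minor wording point. It does not remove the defect: the operative word says something else, and intent has to be inferred from an exception.

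Four stronger readings are tempting, and the documents do not support them.

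- **That the liver screen does not screen at all.** The last row of the table shows otherwise. A patient without Gilbert's Disease who fails every limit is rejected even on the literal reading.
- **That a patient with discordant results is eligible.** The text supports only that such a patient meets criterion 6. Exclusion 3 can still bar entry, inclusion 3 requires recovery from earlier treatment-related toxicity, and Section 8.0 requires clinically significant abnormal results to be repeated within 48 hours of beginning therapy. None of these sets a liver limit, so they reduce the exposure without curing the wording.
- **That the 'or' between AST and ALT is also an error.** Section 8.0 asks for AST and/or ALT, so accepting either one agrees with the testing schedule and looks like a choice.
- **That Section 6.0 shows an established clinical liver hazard.** Its warning rests on animal studies, and the clinical experience reported beside it is reassuring.

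Nor does criterion 7 settle the meaning. Its 'or' links serum creatinine and creatinine clearance, two measures of one function, and says little about how bilirubin and transaminases were meant to combine.

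**Conclusion.** The point holds in a limited form. Criterion 6 as written is satisfied by a patient who exceeds the bilirubin limit but meets the transaminase limit, or the reverse, and this sits badly with the criterion's stated purpose and its Gilbert exemption. No numerical liver limit elsewhere makes up for it.

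The size cannot be derived. The documents give no frequency of discordant liver results in this population, and some such patients may be stopped under exclusion 3. The conclusion rests on the ordinary meaning of 'or'. That both limits were intended is an inference from the text, and only the sponsor can confirm it. This is a low-priority drafting correction to a safety criterion, with no effect on any endpoint, boundary or analysis.

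**What to change.** The sponsor should reconcile the wording of criterion 6 with its purpose. If both limits are meant, replace the 'or' between the bilirubin limit and the transaminase limit with 'and'. If either limit alone was really meant to suffice, say so expressly and explain what the Gilbert exemption then does.

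The limits, the exemption, the provision for hepatic involvement and the AST-or-ALT wording can all stay as they are.

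The cost is one word, made through the amendment route in the Protocol Administration section (signature by the principal investigator and ethics committee approval). No additional test and no recalculation is needed.

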4.0 TREATMENT PLAN

Study Design

This is a Phase II study to evaluate the safety and efficacy of Pacritinib for the treatment of lower-risk MDS patients. The primary efficacy endpoint is the overall response rate (ORR) based on the IWG-2006 criteria, which includes complete remission (CR), partial remission (PR), and major hematologic improvement (HI). Patient's overall response will be assessed after 1 cycle of treatment but no more than after 4 cycles of treatment; cycle length is 28 days. If no response is attained after 4 cycles of treatment or if progression occurs during therapy at any time, the patient is eligible to continue on Pacritinib therapy with the addition of hypomethylating agent therapy (HMA) [Part 2]. A maximum total of 40 evaluable patients (n=40) will be enrolled.

Agent Administration

All patients will be registered through Protocol Data Management System (PDMS) or CORE.

One initial schedule of Pacritinib will be studied: 200 mg orally twice daily (every 12 hours) without regards to per oral (p.o.) intake. Study cycles will be administered every 28 days \pm 5 days or upon resolution of any clinically significant study drug related adverse event (AE) to grade 0-1, whichever occurs first.

Patients will receive the first course of therapy without interruption regardless of degree of myelosuppression unless patients with an un-transfused pre-treatment platelet count $\geq 50 \times 10^9/L$

$10^9/L$ drops to less than $10 \times 10^9/L$. In that case, drug will be held until platelets return $\geq 10 \times 10^9/L$ and resumed at the next lower dose if appropriate. If prolonged myelosuppression is observed with evidence of a hypocellular marrow (marrow cellularity less than 5% without evidence of recurrent MDS) drug will be stopped. Subsequent courses of Pacritinib will be given at the next lower dose, once counts recover. Count recovery will be considered if the ANC is $\geq 1 \times 10^9/L$ and platelets $\geq 50 \times 10^9/L$. For other clinical situations, subsequent courses of therapy will be administered at the discretion of the treating physician. Patients with residual disease may start the next cycle with neutrophil or platelet counts lower than these, if judged to be in the best interest of the patient to initiate the next cycle. The decision to treat should be documented in the patient's medical record.

Patients will be assessed for disease response at the completion of 4 cycles of treatment. If there has been no response to therapy (i.e. stable disease per IWG-2006), or if disease progression is identified, patients will be eligible to continue on the study with the addition of 5-azacitadine or decitabine, with continuation of Pacritinib, in **Part 2** (Pacritinib + HMA). Patients responding to therapy will continue on Pacritinib monotherapy. Patients with disease progression prior to 4 cycles of Pacritinib are also eligible to initiate the Pacritinib + HMA study portion prior to the completion of 4 cycles. In these patients, disease assessment including bone marrow aspiration should be performed prior to the initiation of Part 2. Patients receiving Pacritinib + HMA will be re-assessed for disease response after 4 cycles of *combination* treatment on Part 2. Patients on pacritinib monotherapy in Part 1 who manifest disease progression at any time, including before or after completion of 4 cycles of treatment, can continue on study in Part 2 with the addition of a hypomethylating agent.

The addition of HMA should be initiated on Day 1 of the next Pacritinib treatment cycle whenever possible. HMA dosing and dosing adjustments should be performed according to the approved package insert, or at a dose of decitabine 20mg/m² IV over 1 hour for 5 days every 4 weeks and according to standard of care (see Section 5.0 for rules of dose reduction or delay).

Duration of Therapy

All patients must complete a screening visit, day 1 visits for each new cycle (+/- 5 days), end of treatment visit and whenever possible, an end of study safety visit 28 days after the last dose of Pacritinib (+/- 7 days).

Patients may remain on study for up to 12 months if the patient demonstrates clinical benefit and no excessive toxicity (i.e. no clinically significant study-drug related grade ≥ 3 toxicity). Patients who are experiencing clinical benefit beyond 12 months and have not experienced excessive toxicity may be eligible to continue therapy after discussion with the PI and the discussion documented in the patient's medical record. After the end of therapy and/or 30 days after your last dose of study drug, the study staff will follow your health status by phone call every 2 months (+/- 2 months) until you receive another cancer treatment.

Treatment is expected to continue until one of the following criteria applies:

1. Possibility of undergoing allogeneic bone marrow transplantation
2. Unacceptable adverse event(s)
3. Discontinuation of study drug for more than 6 weeks
4. Clinically significant intercurrent illness that prevents further administration of treatment
5. Patient request
6. General or specific changes in the patient's condition that render the patient unacceptable for further treatment in the judgment of the investigator or treating physician.
7. Note that patients with progressive disease or lack of objective response after 4 cycles of Pacritinib monotherapy are eligible to continue on study with the addition of a hypomethylating agent (azacitadine or decitabine) to Pacritinib. In patients with clinically significant progressive disease and/or lack of objective response after 4 cycles of *combination* therapy, treatment will be discontinued.

After the first course of therapy, interval between cycles of therapy can be spaced out at the discretion of the treating physician, although a schedule as close as possible to the proposed one should be attempted.

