Disease progression	
For patients with:
 
 • Less than 5% blasts: $\geq 50\%$ increase in blasts to $> 5\%$ blasts • 5%-10% blasts: $\geq 50\%$ increase to $> 10\%$ blasts • 10%-20% blasts: $\geq 50\%$ increase to $> 20\%$ blasts • 20%-30% blasts: $\geq 50\%$ increase to $> 30\%$ blasts 
Any of the following:
 
 • At least 50% decrement from maximum remission/response in granulocytes or platelets • Reduction in Hgb by ≥ 2 g/dL • Transfusion dependence
Survival	
Endpoints:
 
 • Overall: death from any cause • Event free: failure or death from any cause • PFS: disease progression or death from MDS • DFS: time to relapse

- Cause-specific death: death related to MDS

Table 10. Proposed modified International Working Group response criteria for hematologic improvement⁷

Hematologic improvement [*]	Response criteria (responses must last at least 8 wk) [†]
Erythroid response (pretreatment, < 11 g/dL)	Hgb increase by ≥ 1.5 g/dL Relevant reduction of units of RBC transfusions by an absolute number of at least 4 RBC transfusions/8 wk compared with the pretreatment transfusion number in the previous 8 wk. Only RBC transfusions given for a Hgb of ≤ 9.0 g/dL pretreatment will count in the RBC transfusion response evaluation [†]
Platelet response (pretreatment, < $100 \times 10^9/L$)	Absolute increase of $\geq 30 \times 10^9/L$ for patients starting with $> 20 \times 10^9/L$ platelets Increase from $< 20 \times 10^9/L$ to $> 20 \times 10^9/L$ and by at least 100% [†]
Neutrophil response (pretreatment, < $1.0 \times 10^9/L$)	At least 100% increase and an absolute increase $> 0.5 \times 10^9/L$ [†]
Progression or relapse after HI [‡]	At least 1 of the following: At least 50% decrement from maximum response levels in granulocytes or platelets Reduction in Hgb by ≥ 1.5 g/dL Transfusion dependence

Secondary endpoints include:

1. To evaluate efficacy of Pacritinib based on the presence of JAK2 and FLT3 mutations at diagnosis.
2. To evaluate efficacy based on IPSS, R-IPSS and LR-MDS risk classification systems at diagnosis.

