All patients who received any dose of the study agent will be included in the analysis for efficacy and safety. Demographic/clinical characteristics (i.e. including duration of response) and safety data of the patients will be summarized using descriptive statistics such as mean, standard deviation, median and range. For the primary efficacy analysis, we will estimate the ORR for the Pacritinib and Pacritinib + HMA, along with the 95% confidence interval. Patients who drop out of the study before completing all the cycles will be treated as “failures” for the primary analysis. Overall response rate (ORR) during the study period will also be presented with the 95% confidence interval. The association between ORR and patient’s clinical characteristics will be examined by Wilcoxon’s rank sum test or Fisher’s exact test, as appropriate. Toxicity type, severity and attribution will be summarized for each patient using frequency tables. The distribution of time-to-event endpoints (EFS and OS) including overall survival and event free survival will be estimated using the method of Kaplan and Meier. Comparisons of time-to-event endpoints by important subgroups will be made using the log-rank tests. The additional treatment in part 2 will be included in time-to-event analysis as time-dependent covariates.

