- Important medical events as defined above, may also be considered serious adverse events. Any important medical event can and should be reported as an SAE if deemed appropriate by the Principal Investigator or the IND Sponsor, IND Office.
- All events occurring during the conduct of a protocol and meeting the definition of a SAE must be reported to the IRB in accordance with the timeframes and procedures outlined in the University of Texas M. D. Anderson Cancer Center Institutional Review Board Policy

for Investigators on Reporting Unanticipated Adverse Events for Drugs and Devices. Unless stated otherwise in the protocol, all SAEs, expected or unexpected, must be reported to the IND Office, regardless of attribution (within 5 working days of knowledge of the event).

- All life-threatening or fatal events, that are unexpected, and related to the study drug, must have a written report submitted within 24 hours (next working day) of knowledge of the event to the Safety Project Manager in the IND Office.
- Unless otherwise noted, the electronic SAE application (eSAE) will be utilized for safety reporting to the IND Office and MDACC IRB.
- Serious adverse events will be captured from the time of the first protocol-specific intervention, until 30 days after the last study treatment/intervention, unless the participant withdraws consent. Serious adverse events must be followed until clinical recovery is complete and laboratory tests have returned to baseline, progression of the event has stabilized, or there has been acceptable resolution of the event.
- Additionally, any serious adverse events that occur after the 30 day time period that are related to the study treatment must be reported to the IND Office. This may include the development of a secondary malignancy.
 - Serious adverse events will be forwarded to FDA by the IND Sponsor (Safety Project Manager IND Office) according to 21 CFR 312.32.

It is the responsibility of the PI and the research team to ensure serious adverse events are reported according to the Code of Federal Regulations, Good Clinical Practices, the protocol guidelines, the sponsor's guidelines, and Institutional Review Board policy.

Reporting of external SAEs

- The MDACC institutional policy for reporting of external SAEs will be followed.

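### Post-treatment calls stop once a patient receives another cancer treatment, yet Kaplan-Meier overall survival is planned; later deaths would be lost and any censoring there is likely informative

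*Combined protocol and SAP*

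**What the plan says.** Section 4.0 (Duration of Therapy) sets the only post-treatment follow-up: "the study staff will follow your health status by phone call every 2 months (+/- 2 months) until you receive another cancer treatment".

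The survival block of Table 9 (Section 10.0) lists OS as "Overall: death from any cause", with no restriction to deaths before new therapy. The Statistical Analysis Plan in Section 12.0 says that "time-to-event endpoints (EFS and OS) including overall survival and event free survival will be estimated using the method of Kaplan and Meier" and that "Comparisons of time-to-event endpoints by important subgroups will be made using the log-rank tests". It gives no censoring rule for OS. Its one provision for further therapy concerns the hypomethylating agent (HMA) added on study: "The additional treatment in part 2 will be included in time-to-event analysis as time-dependent covariates". Therapy given off study is not mentioned.

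Section 13.0 captures serious adverse events "until 30 days after the last study treatment/intervention, unless the participant withdraws consent"; after that window only treatment-related events must be reported.

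**The concern.** What is collected does not match what is to be analysed. OS counts all deaths, but the plan stops asking about a patient's status at an event that can come long before death. Followed as written, a patient who starts off-study therapy would in practice be censored around that date.

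Kaplan-Meier and log-rank methods need censoring that is unrelated to the risk of death. The patients affected here are a selected group. Among the reasons for ending treatment, Section 4.0 includes "Possibility of undergoing allogeneic bone marrow transplantation" and unacceptable adverse events, and it ends treatment for this group: "In patients with clinically significant progressive disease and/or lack of objective response after 4 cycles of" combination therapy. Others may decline Part 2. Poor-prognosis exits would tend to make OS look too good; transplant exits could work the other way. If switching differs between subgroups, the log-rank comparisons would be distorted too.

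**Working it through.** **Is vital status collected anywhere else?**

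- Section 8.0 (End-of-Treatment): one assessment about 28 days after the last dose, with no survival item.
- Section 9.0 (Table 8): no survival item.
- Section 11.0: reasons for removal only, no follow-up.
- Section 13.0: serious adverse events for 30 days, then only related ones. A related late death would be reported, but this is not survival follow-up.
- Part 2 HMA is study treatment, so starting it does not end follow-up. Only off-study therapy does.

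No other source of vital status is planned.

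**How large could the error be?** The plan states no OS figure to reproduce, so this is an illustration with constant hazards.

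Inputs:

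- Death hazard before switching: b = ln 2 / median. Section 2.1 gives natural-history medians of 3.5 years (Int-1) and 5.7 years (Low). Using them here is an assumption. b = 0.198 or 0.122 per year.
- Switching to off-study therapy: a = −ln(1 − p), with p assumed to be 20%, 40% or 60% per year. For 40%, a = 0.511.
- Death hazard after switching: c = HR × b, with HR assumed to be 0.5, 1, 2 or 3.
- Start of switching: d = 0, or d = 8 × 28 = 224 days = 0.613 years (four monotherapy plus four combination cycles). Early exits occur, but Part 2 non-response is judged only after four combination cycles, so the two starts are best read as bounds.

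Formulas, with u = t − d:

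- Kaplan-Meier censored at switching estimates exp(−b·t).
- True OS = exp(−b·d) × {exp(−(a+b)u) + a[exp(−c·u) − exp(−(a+b)u)] / (a+b−c)}.

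Worked example: 3.5-year median, 40% per year, HR 2, t = 2 years.

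- Censored estimate: exp(−0.396) = 67.3%.
- d = 0: 0.2423 + 1.633 × (0.4529 − 0.2423) = 58.6%. Error: 67.3 − 58.6 = +8.7 points.
- d = 0.613: 0.8856 × {0.3742 + 1.633 × (0.5774 − 0.3742)} = 62.5%. Error: +4.8 points.

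Error in OS (censored estimate minus truth, in points) for the 3.5-year median and 40% per year:

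| Time | Switching starts | HR 0.5 | HR 1 | HR 2 | HR 3 |
|---|---|---|---|---|---|
| 1 year | after 8 cycles | −0.3 | 0 | +0.6 | +1.1 |
| 1 year | day 0 | −1.8 | 0 | +3.3 | +6.2 |
| 2 years | after 8 cycles | −2.8 | 0 | +4.8 | +8.7 |
| 2 years | day 0 | −5.4 | 0 | +8.7 | +15.2 |
| 3 years | after 8 cycles | −6.0 | 0 | +9.3 | +16.0 |
| 3 years | day 0 | −9.0 | 0 | +13.0 | +21.5 |

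Over both medians, both starts and all three switching rates, the 2-year error is −7.8 to −1.0 at HR 0.5, 0 at HR 1, +1.7 to +12.5 at HR 2, and +3.3 to +21.8 at HR 3. A simulation of 2,000,000 patients agrees with the closed form within 0.2 points.

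**Information lost even without bias.** At HR 1 and d = 0, recorded 2-year deaths are b/(a+b) × (1 − 0.2423) = 0.2794 × 0.7577 = 21.2% of patients, out of 32.7% who die; 35% of deaths go unrecorded. With d = 0.613, recorded deaths are 0.1144 + 0.8856 × 0.2794 × (1 − 0.3742) = 26.9%, and 18% go unrecorded.

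**Scale.** With n = 40 and 2-year OS of 67.3%, the 95% half-width is about 1.96 × √(0.673 × 0.327 / 40) = 14.5, or roughly 15 points.

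**The case against.** The bias is conditional. No passage says OS is censored at new therapy; what is documented is that follow-up ends there and that the censoring rule is missing. The switching rate, hazard ratio, start time and time horizon are all assumed, and the plan names no landmark for OS. At 1 year with the later start the error is at most 1.1 points in the central case, and at HR 1 it vanishes at every horizon. Because patients who do not respond to monotherapy can receive an HMA on study, heavy switching from day 0 is an aggressive scenario. With the later start and HR 2, the 2-year error is about a third of the confidence half-width.

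OS also matters little here. Response rate is the primary endpoint, OS is not among the two secondary endpoints listed in Section 10.0, and the survival definitions come from a general response-criteria table.

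All of this stands as a limit on size and importance. It does not remove the mismatch. The plan commits to OS and to subgroup tests on it, and stops collecting the data they need in a selected group. Finding later deaths informally from hospital records is not planned, and could add its own bias if deaths come to light more readily than survival is confirmed. Any bias adds to sampling error, and the confidence interval would not show it.

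**Conclusion.** The concern holds. Section 4.0 ends follow-up at a prognosis-related event, and Sections 10.0 and 12.0 plan an all-cause OS analysis that needs follow-up beyond it. If OS is censored there, independent censoring is doubtful. Upward bias is likely after treatment failure, but the documents do not establish the net direction.

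Under the stated assumptions the central 2-year error at HR 2 lies between +4.8 and +8.7 points, with −5.4 to −2.8 at HR 0.5 and none at HR 1. Even with no bias, about 18% to 35% of 2-year deaths would go unrecorded. Consequences are limited to the descriptive OS curve and its subgroup comparisons. The response rate and the stopping rules are unaffected. This should be corrected, but it does not threaten the primary result.

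**What to change.** **Section 4.0, Duration of Therapy:** collect survival status by phone until death, withdrawal of consent or a stated study cut-off, regardless of later therapy, and record the date and type of that therapy.

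**Section 12.0, Statistical Analysis Plan:** state that OS is not censored at subsequent therapy, that patients not known to have died are censored at the date last known alive, and that censoring at subsequent therapy is a sensitivity analysis only.

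A separate point of detail, which carries no weight in the verdict: the plan promises Part 2 treatment as a time-dependent covariate but names no regression model. Keep the log-rank test for baseline subgroups and name a Cox model with HMA start as the time-dependent term.

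**Cost:** a few sentences, plus about six calls per switched patient per year at the existing two-month interval, in a trial of at most 40 evaluable patients. The total depends on the cut-off chosen. The current sentence addresses the patient directly, so patient-facing text may need the same change.
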